Sample size	
Based on the endpoint of change in LAVI over 18 months, the PARABLE trial aims to recruit 250 subjects (125 per arm). Sample size estimates were calculated from the current STOP-HF subject database (n=1499). A subsample of subjects with BNP > 50 pg/mL, LAVI > 28 mL/m², with normal ejection fraction ($\geq 50\%$) and in normal sinus rhythm was drawn. This resulted in a population of 163 (11%) of the total with a population BNP of 125 pg/mL and a baseline mean LAVI of 36.2 mL/m² (standard deviation of 6.9 mL/m²) determined by Doppler Echocardiography. This LAVI is reassuringly similar to the baseline level observed by Solomon et al. (Lancet 2012; 380: 1387–95) in the PARAMOUNT study, which observed a 36-week drop in LAVI of 2.6 mL/m². Assuming the control group shows no decrease in LAVI (as in Solomon et al. 2012 paper), the expected effect size in a similar study is $2.6/6.5 = 0.38$. Setting alpha = 5% (two-tailed),

	
beta = 20% and using an independent t-test to assess the change in LAVI over follow-up, the required number of subjects to detect this effect is 222 (111 per study arm), or 248 after accounting for a 10% dropout rate.
 
In a review of the expected effect size, once blinded echocardiography was available for 125 patients at the 9-month time point, it was noted that the actual standard deviation of baseline to 9-month change scores was 4.7. This means an expected effect size of at least $(2.0/5.0) = 0.40$. An effect size of 0.4 would require 96 patients in each group, suggesting that the study is adequately powered on LAVI assessed by echocardiography. In addition, the study has at least 80% power with a two-tailed alpha = 5% to detect a 6 g/m² difference in LVMI change by CMRi, a 2.5 mL/m² in LAVI difference by CMRi, a 2-unit difference in E/e' or e' using Tissue Doppler measurements.

--	---

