16.2 Determination of sample size

Based on the endpoint of change in LAVI over 18 months, the PARABLE trial aims to recruit 250 subjects (125 per arm). The current STOP-HF database includes 1499 subjects with cardiovascular risk factors. An additional cohort of just under 1000 subjects has been recruited from the STOP-HF outreach service and is available for screening and recruitment into the study. The STOP-HF Investigators are also working with other clinical trial units and can incorporate additional centres if required to achieve timely recruitment.

Sample size estimates were calculated from the current STOP-HF subject database (n=1499). A subsample of subjects with BNP > 50 pg/mL, LAVI > 28 mL/m², with normal EF (\geq 50%) and in normal sinus rhythm was drawn. This resulted in a population of 163 (11%) of the total with a population BNP of 125 pg/mL and a baseline mean LAVI of 36.2 mL/m² (standard deviation of 6.9 mL/m²) determined by Doppler

Echocardiography. This LAVI is reassuringly similar to the baseline level observed by Solomon et al. (Lancet 2012; 380: 1387–95) in the PARAMOUNT study, which observed a 36-week drop in LAVI of 2.6 mL/m², and assuming the control group shows no decrease in LAVI (as in Solomon et al. 2012 paper), the expected effect size in a similar study is $2.6/6.5 = 0.38$. Setting alpha = 5% (two-tailed), beta = 20% and using an independent t-test to assess the change in LAVI over follow-up, the required number of subjects to detect this effect is 222 (111 per study arm), or 248 after accounting for a 10% dropout rate.

In a review of the expected effect size, once blinded echocardiography was available for 125 patients at the 9-month time point, it was noted that the actual standard deviation of baseline to 9-month change scores was 4.7. This means an expected effect size of at least $(2.0/5.0) = 0.40$. An effect size of 0.4 would require 96 patients in each group, suggesting that the study is adequately powered on LAVI assessed by echocardiography. In addition, the study has at least 80% power with a two-tailed alpha = 5% to detect a 6 g/m² difference in LVMI change by CMRi, a 2.5 mL/m² in LAVI change by CMRi, a 2-unit difference in E/e' or e' using Tissue Doppler measurements.

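### Section 16.2 and the synopsis print two sample-size figures that do not follow from their own inputs: 2.6/6.5 given as 0.38, and 96 per group for an effect size of 0.40

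*Combined protocol and SAP*

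**What the plan says.** Section 16.2 sizes the trial in two steps, and the sample-size entry of the synopsis (section 7) repeats both.

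The initial calculation draws a subsample from the STOP-HF database with a "baseline mean LAVI of 36.2 mL/m² (standard deviation of 6.9 mL/m²) determined by Doppler" echocardiography. It takes a fall of 2.6 mL/m² on LCZ696 and none on control, and states that "the expected effect size in a similar study is $2.6/6.5 = 0.38". The error rates and test are then given: "Setting alpha = 5% (two-tailed), beta = 20% and using an independent t-test to assess the change in LAVI over follow-up". The result is that "the required number of subjects to detect this effect is 222 (111 per study arm), or 248 after accounting for a 10% dropout rate". Planned recruitment is 250, or 125 per arm.

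The second step is a blinded review of 9-month echocardiograms in 125 patients, where "it was noted that the actual standard deviation of baseline to 9-month change scores was 4.7". The plan takes 2.0/5.0 = 0.40 as the effect size and concludes: "An effect size of 0.4 would require 96 patients in each group, suggesting that the study is adequately powered on LAVI assessed by echocardiography". The synopsis has the same words: "An effect size of 0.4 would require 96 patients in each group". The sentence with the 96 gives no alpha or power. The next sentence, on other endpoints, again uses 80% power and a two-tailed 5% level.

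**The concern.** These are the figures on which the plan rests its claim of adequate size, so a reader should be able to recompute them.

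The first equation cannot be right as printed, because its divisor and its quotient imply different sample sizes. Someone who works from 6.5 arrives at 99 to 100 per arm rather than 111. The second figure is presented as the number required for an effect size of 0.40, yet it falls 3 to 4 per group short of that requirement. What is at stake is whether the written justification can be reproduced, and whether the planned 250 still stands once both figures are corrected.

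**Working it through.** **Inputs, all from section 16.2:** fall in LAVI 2.6; printed divisor 6.5; baseline SD 6.9; observed SD of 9-month change 4.7; revised effect 2.0/5.0; two-sided alpha 5%; power 80%; independent t-test; 1:1 allocation; 10% dropout; 250 planned. Alpha and power are assumed to apply to the 96 as well, since no other values appear in the section.

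**Formula.** Normal approximation: n per group = 2(z₀.₉₇₅ + z₀.₈₀)²/d² = 2(1.960 + 0.842)²/d² ≈ 15.70/d². The t-test figures use the noncentral t distribution.

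| Effect size d | Normal | t-test |
|---|---|---|
| 2.6/6.9 = 0.377 | 110.6 → 111 | 111.5 → 112 |
| 0.38 exactly | 108.7 → 109 | 109.7 → 110 |
| 2.6/6.5 = 2.0/5.0 = 0.400 | 98.1 → 99 | 99.1 → 100 |
| 2.0/4.7 = 0.426 | 86.7 → 87 | 87.7 → 88 |

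**Reproducing the plan's 111 and 248.** SD 6.9 with the normal approximation gives 111 per arm exactly. Then 111/0.9 = 123.3, so 124 per arm and 248 in total. Both stated figures are recovered.

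**First slip.** 2.6/6.5 = 0.400. For the quotient to round to 0.38, the SD must lie between 2.6/0.385 = 6.75 and 2.6/0.375 = 6.93. The value 6.9 lies in that range and 6.5 does not. Taken literally, 6.5 gives 99 or 100 per arm, which is 198/0.9 = 220 or 200/0.9 = 222.2, so 223, recruited.

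**Second slip.** No usual variant at d = 0.40 gives 96:
- z values rounded to 1.96 and 0.84: 98.0
- the shortcut 16/d²: 100
- a one-sided test: 78
- the t-test figure inflated for a Wilcoxon test (efficiency 0.955): 104

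Solving backwards, 96 per group corresponds to d = 0.404 (normal) or 0.406 (t-test). At d = 0.40, 96 per group has power 79.1% (normal) or 78.7% (t-test).

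**Effect on the planned 250.** 125 × 0.9 = 112.5, taken as 112 completers per arm. Power by the t-test:
- d = 0.426: 88.7%
- d = 0.40: 84.6%
- d = 0.38: 80.8%
- d = 0.377: 80.2%

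**The case against.** The strongest defence concerns the 96. It says that 0.40 may be a rounded value: by the normal approximation 96 matches d = 0.404, which rounds to 0.40. The plan also offers its value as a floor ("This means an expected effect size of at least $(2.0/5.0) = 0.40") and uses an SD of 5.0 where 4.7 was observed. With 2.0/4.7 = 0.426 only 87 to 88 per group are needed, and 96 would give 83.5% power. The sentence states no power of its own, and 78.7% is close to 80%.

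Part of this stands. The adequacy conclusion for echocardiographic LAVI survives, and the shortfall is small. The rounding argument does not stand: the ratio is printed as 2.0/5.0, which is exactly 0.40, and the test named in the section is a t-test, for which even 0.405 needs 97. The sentence pairs 96 with 0.4, and that pairing is wrong.

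On the first slip, a reader who ignores the divisor and uses 0.38 gets 109 or 110, close to 111. That is fair, but the printed equation is still false. It appears identically in two places, so a fault in reading the PDF is unlikely.

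A last objection is that nothing practical turns on this. For enrolment and analysis that is correct: section 25.1 places the last patient's first visit in December 2018 and the last treatment-period visit in December 2020.

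**Conclusion.** Both figures are wrong as written, in section 16.2 and in the synopsis. The equation misstates either its divisor or its quotient. The divisor is the likelier slip, because 6.9 is the only SD printed in that calculation and it recovers 111, but this is an inference for the sponsor to confirm. The 96 is low by 3 (normal approximation) or 4 (t-test) per group, assuming the section's two-sided 5% and 80% power apply to it.

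A reader might infer that the trial is undersized. The documents do not support that: on their echocardiographic effect sizes and 10% dropout, the planned 250 keeps at least 80% power. The margin is thin at 0.377 (80.2%) and wider at 0.40 (84.6%).

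The opposite inference, that power is therefore secure for the primary endpoint, is not supported either. That endpoint is LAVI by cMRI over 18 months, and every figure checked here is echocardiographic. Section 16.2 also claims 80% power for a 2.5 mL/m² difference in LAVI change by cMRI, but shows neither an SD nor a number of patients for it. That claim cannot be checked, and it is not shown to be wrong.

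Severity: minor.

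**What to change.** Make the corrections in both section 16.2 and the synopsis, and use one method throughout.

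- Print in the effect-size equation the SD actually used. If 6.9 is confirmed, the equation becomes 2.6/6.9 = 0.38. If it was another value, recompute from that value.
- Under the t-test that the section names, replace 96 with 100 per group. If 6.9 is confirmed, also replace 111 per arm with 112, which is 224 in total. After 10% dropout this becomes 224/0.9 = 248.9, so 249, or 250 when rounded up within each arm (112/0.9 = 124.4, so 125). Both are within the planned 250.
- Alternatively, state that the normal approximation was used. Then print 99 in place of 96 and, if 6.9 is confirmed, keep 111, 222 and 248.
- State the alpha and power next to the revised per-group figure.

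The cost is a few text edits, with no effect on enrolment, data collection or analysis. Section 15.1 requires a written, approved amendment for any protocol change, while section 22.4 lets non-substantial amendments take effect immediately.

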17. DIRECT ACCESS TO SOURCE DATA/DOCUMENTS

Direct access will be granted to authorised representatives from the Sponsor, host institution and the regulatory authorities to permit trial-related monitoring, audits and inspections.

18. DATA HANDLING AND RECORD KEEPING

18.1 Data collection, source documents and case report forms (CRFs)

Source documents for this study will include hospital records, procedure reports and data collection forms (e.g. questionnaires). These documents will be used to enter data on the CRFs.

A paper CRF will be used for this study. All data entered on CRFs must be entered legibly. If an error is made, the error will be crossed through with a single line in such a way that the original entry can still be read. The correct entry will then be clearly inserted and the alterations will be initialled and dated by the Investigator.

Data reported on the CRF that are derived from source documents must be consistent with the source documents or the discrepancies must be explained. In some instances it is acceptable to file a copy of the source document (e.g. blood report, ABPM read-out) in the study file and to cross-reference to the source document in the CRF.

The monitor must make certain that all data are completed on the CRF. After comparing the data to the source documents, the monitor will request correction/clarification from the Investigator.

After the last visit of the subject, the Investigator must attest the authenticity of the data collected in the CRF by signing the appropriate section of the CRF.

All documents will be stored safely in a confidential manner. On all study-specific documents, other than informed consent, the subject will be referred to by the subject study number/code.

18.2 Data reporting

Subjects will be identified by a study specific subject number in the database. The name and any other identifying detail will not be included in any study data electronic file.

19. RETENTION OF ESSENTIAL DOCUMENTS

Essential documents will be retained until at least 15 years after the publication of the clinical study report. These documents will be retained for a longer period however, if required by the applicable regulatory requirements or by agreement with the Sponsor. The Investigator should retain the trial-related essential documents as required by the applicable regulatory requirements and until the Sponsor informs the Investigator these documents are no longer necessary.

20. QUALITY CONTROL AND QUALITY ASSURANCE PROCEDURES

The study will be conducted in accordance with the current approved protocol, ICH good clinical practice (GCP), relevant regulations and applicable SOPs.

20.1 Before the study

The Investigator will allow the monitor to visit the site and facilities where the study will take place in order to ensure compliance with the protocol requirements.

Training sessions will be organised for the Investigators/study team on the study protocol.

20.2 During the study

For all participants who give informed consent, regardless of whether or not they receive any study drug, the Investigator designee will record participant identification data in the "Participant Identification List" (full name, initials, date of birth, participant identification code) or other similar list. The participant identification list will allow for the definite identification of any research participant that takes part in the study. A statement acknowledging the participation of a research participant in this clinical study will be also documented in the participant's medical file/notes.

To protect the research participant's identity a unique identification code (randomisation number/study ID) will be assigned by WebEz to each study participant and used in lieu of the participant's name when AEs and/or other study-related data are reported. This coded form of identification, instead of the participant's name, will appear on all documents/databases and will be cross-referenced by the participant's

date of birth. Documents not for submission to Sponsor, such as the confidential participant identification list and the signed Informed Consent Forms, will be kept in strict confidence on site and will not be removed from site.

Personal information will be treated as confidential but may need to be reviewed by authorised representatives of the Sponsor - such as monitors and auditor/inspector from the ECs and the regulatory authorities. The participant's consent to direct access to his/her original medical records for data verification purposes will be obtained, via the informed consent process prior to that participant's participation in the study.

The Investigator will permit the Sponsor, authorised agents of the Sponsor (such as monitors, auditors, etc.), the Contract Research Organization, and regulatory agency employees to enter and inspect any site where the drug or records pertaining to the drug are held, and to inspect and copy all records relating to an investigation, including research participant records.

The Investigator will make available all CRFs for review by the Sponsor, study monitor, and the regulatory agencies as necessary. To ensure the accuracy of data submitted, it is mandatory that representatives of the Sponsor and of the regulatory agencies have access to source documents (i.e. participant medical records or notes, charts, laboratory reports, etc.). Participant confidentiality will be protected at all times. The Investigator will allow the monitor to:

- inspect the site, the facilities and the material used for the study
- meet all members of his/her team involved in the study
- consult all of the documents relevant to the study
- have access to the CRFs
- check that the CRFs have been filled out correctly
- directly access source documents for comparison of data therein with the data in the CRFs
- verify that the study is carried out in compliance with the protocol and local regulatory requirements

The study Investigators will adhere to hospital protocols pertaining to healthcare record use and storage. The Investigators and authorised designees will ensure that the confidentiality of the participants' data is preserved. On CRFs or any other documents submitted to the Sponsor's designee, the participant will be identified not by their names, but by their coded form of identification.

21. AUDITS AND INSPECTIONS

The trial may be subject to internal or external auditing or inspection procedure to ensure adherence to GCP. Access to all trial-related documents will be given at that time.

A quality assurance audit may be conducted by the Sponsor or its agent at any time during, or shortly after, the study. The Investigator will permit an independent audit by an auditor mandated by Sponsor, after reasonable notice. The purpose of an audit is to confirm that the study is conducted as per protocol, GCP and applicable regulatory requirements, that the rights and well-being of the patients enrolled have been protected, and that the data relevant for the evaluation of the IMP have been captured, processed and reported in compliance with the planned arrangements. The Investigator will permit direct access to all study documents, drug accountability records, medical records and source data.

Regulatory authorities may perform an inspection of the study up to several years after its completion. If an inspection is announced the Sponsor will be informed immediately.

22. ETHICAL CONSIDERATIONS

22.1 Ethical conduct of the study

This study will be carried out in compliance with the Study Protocol and in accordance with the Sponsors SOPs. These are designed to ensure adherence to GCP guidelines, as described in:

- International Conference on Harmonization (ICH) of Technical Requirements for Registration of Pharmaceuticals for Human Use Harmonized Tripartite Guidelines for Good Clinical Practice 1996
- EU CT Directive 2001/20/EC
- GCP Commission Directive 2005/28/EC
- Declaration of Helsinki, concerning medical research in humans (1964) including all amendments up to and including the 2013 revision
- National laws

The Investigator agrees, when signing the study protocol, to adhere to the instructions and procedures described in it and to the principles of GCP to which it conforms. The regulatory permission to perform the study will be obtained in accordance with applicable regulatory requirements. All ethical and regulatory approvals must be available before a patient is exposed to any study-related procedure, including screening tests to determine eligibility.

22.2 Declaration of Helsinki

The Sponsor will ensure that this study is conducted in accordance with the ethical principles that have their origins in the Declaration of Helsinki.

22.3 Good Clinical Practice

This study will be conducted in accordance with GCP, as defined by the ICH and in accordance with the ethical principles underlying EU Directive 2001/20/EC and 2005/28/EC.

22.4 Approvals

Before initiating this study, the protocol, SmPC, Investigators Brochure, Patient Information Leaflet and Informed Consent Form, and any other written information to be given to participants will be reviewed and approved by the competent authority and the EC.

A signed and dated statement that all documents submitted for review have been approved by the EC will be given to the Sponsor or designee before the study can commence at a site. The membership and the constitution of the EC who approved the documents will be also supplied to the Sponsor or designee.

The Sponsor/designee will submit and obtain approval from the above parties for substantial amendments to the original approved documents.

Modifications of the signed protocol are only possible by approved protocol amendments and with the agreement of all responsible persons. The procedure for approval of a protocol amendment is identical to that for approval of the protocol. All substantial protocol amendment must be submitted to the Regulatory Authority and EC for approval. The changes in the protocol must not be instituted until the amendment and the revised informed consent (if appropriate) has been reviewed and received approval / favourable response from both the Regulatory Authority and EC. A protocol amendment intended to eliminate an apparent immediate hazard to participants may be implemented immediately providing that both the Regulatory Authority and EC are notified as soon as possible, and an approval is requested. Non-substantial protocol amendments may be implemented immediately.

22.5 Informed consent

The Investigator or his/her designee shall obtain written informed consent from each participant before his/her participation in the study and before any study related procedure is undertaken. Therefore, informed consent shall be obtained at Visit 1 before any study related procedure is performed. Prior to this, the Investigator or his/her delegate must inform each participant of the objectives, benefits, risks and requirements imposed by the study, as well as the nature of the study drugs. Informed consent must also be obtained for each patient to allow biobanking of blood samples.

A separate signature page is included on the Participant Information and Consent Form for this purpose. Only a qualified medical doctor may obtain informed consent.

The participant will be provided with an information and consent form in clear, simple language. He/she must be allowed ample time to inquire about details of the study and to decide whether or not to participate in the study. The Investigator shall answer all questions the patient may have about the study.

Two original information and consent forms must be completed, dated and signed personally by the participant and by the person responsible for collecting the informed consent. The participant will be given one signed original information and consent form, the second original will be kept by the Investigator.

Any change to the information and consent form constitutes an amendment to this document and must be submitted for approval to the EC, and if applicable to the Regulatory Authorities. Such amendments may only be implemented after written approval of the EC has been obtained and compliance with the local regulatory requirements, with the exception of an amendment required to eliminate an immediate risk to the study participants.

Each participant affected by the amendment or an independent witness must complete, date and sign two originals of the new version of the information and consent form together with the person who conducted the informed consent discussion. He/she will receive one signed original amendment to the information and consent form.

The obtaining of informed consent and any pre-consent discussions should be documented in the patients' medical notes. The following should be recorded in the subject's medical file:

- The date that the Informed Consent Form was given to the subject
- The date written informed consent was obtained
- The name of the person obtaining informed consent
- Any other relevant information regarding the consent process

For every patient recruited into the PARABLE clinical trial, a notification should be placed on the inside of the front cover of the patients' medical notes in order to identify the clinical trial. (The notification should record the study name, patients study ID, consent date, the 'end of patient participation date' which should be completed at visit 11, the name of the Principal Investigator and contact number of the research team).

